## LIST OF ABBREVIATIONS

AE	Adverse Event
AFP	α-fetoprotein
AUC	Area Under the Curve
BMI	Body Mass Index
СРК	Creatine Phosphokinase
CSMC	Cedars Sinai Medical Center
CTCAE	Common Terminology Criteria for Adverse Events
CTMS	Clinical Trials Management System
DSMB	Data Safety Monitoring Board
EU	Emory University
HCC	Hepatocellular Carcinoma
HCV	Hepatitis C Virus
HR	Hazard Ratio
LI-RADS	Liver Imaging Reporting and Data System
LRTs	Locoregional Therapies
LT	Liver Transplantation
MELD	Model for End Stage Liver Disease
MRE	Magnetic Resonance Elastography
mRECIST	Modified Response Evaluation Criteria in Solid Tumors
MRI	Magnetic Resonance Imaging
MRI-PDFF	Proton Density Fat Fraction
NASH	Nonalcoholic Steatohepatitis
NWU	Northwestern Memorial Hospital
ORA	Office of Regulatory Affairs
OPTN	Organ Procurement and Transplantation Network
OS	Overall survival
PT/INR	Prothrombin Time
QMC	Quality management core
RCT	Randomized Control Trial
RFA	Radiofrequency Ablation
RFS	Recurrence-Free Survival
SAE	Serious Adverse Event
sCD163/14	Soluble Cluster Differentiation 163/14
SOC	System Organ Class
sTNFR I/II	Soluble Tumor Necrosis Factor Receptor I/II
TAC	Treatment Assignment Code
TACE	Transarterial Chemoembolization
TGFβ1	Transforming Growth Factor-β1
TTR	Time to Recurrence
UCLA	University of California, Los Angeles
UCSF	University of California, San Francisco
UNOS	Milan/United Network for Organ Sharing

#### STUDY SCHEMA

Patients with compensated liver cirrhosis with early stage hepatocellular carcinoma (HCC) Tumor burden within Milan Criteria or OPTN tumor downstaging criteria at staging scan (CT or MRI) Initial locoregional therapy with verification of adequate response

# Pre-Screen Chart Review – Initial determination of eligibility (N=162; 33 at CSMC, 32 at UCLA, 32 at NWU, 32 at UCSF, and 32 at EU)

Medical charts of patients with HCC reviewed for cirrhosis diagnosis, prior or current statin use, prohibited concomitant medications, medical contraindications, laboratory results, size and number of tumors from staging scan (confirm meeting Milan Criteria or OPTN tumor downstaging criteria), first liver directed therapy followed by an MRI or CT to verify HCC response. A study information packet that includes an introductory letter, leaflet, consent and HIPAA forms will be mailed to potentially eligible patients. Study coordinator will call all potentially eligible patients to introduce the study and answer questions.

Screening Visit – Consent and Final determination of eligibility (N=144; 29 at CSMC, 28 at UCLA, 28 at NWU, 28

at UCSF, and 28 at EU)

Patients who are eligible based on pre-screen chart review will be consented into the trial before any research procedures are initiated. Study physician will thoroughly review the patient's medical history and medications and evaluate all inclusion/exclusion criteria. Patients will undergo blood tests to confirm eligibility and safety of statin initiation; urine pregnancy test for women able to become pregnant. Patients with a MELD score  $\geq 30$  or, AST/ALT > 5x ULN; and women who are pregnant will be excluded.

**Eligible, consented patients with HCC randomized to pravastatin or placebo (N=130; 26 per site)** Pravastatin 40 mg, daily for 12 months Placebo identical in color, consistency, and appearance to

statin 40 mg, daily for 12 months	Placebo identical in color, consistency, and appearance
(N=65)	pravastatin 40 mg, daily for 12 months (N=65)

Study Visit 1 – Baseline / initiation of intervention (0-30 days following Screening Visit)

Review medical history, medications, and laboratory test results; symptom assessment; ECOG performance status; blood draw; MRE with fat fraction or FibroScan for liver stiffness testing review inclusion/exclusion criteria; interviewer-administered questionnaire; dispense study drug and diary

#### Study Visit 2 (30 days ± 5 days after initiation of intervention)

[figure not shown]
Review medical history, medications, and laboratory test results; symptom assessment; ECOG performance status; blood draw; collect study drug and diary; assess compliance (pill count); review study diary; assess adverse events; review inclusion/exclusion criteria; dispense study drug and diary

#### Study Visit 3 (3 months ± 15 days following initiation of intervention)

Review medical history, medications, and laboratory test results; symptom assessment; ECOG performance status; blood draw; MRI or CT for HCC surveillance; collect study drug and diary; assess compliance (pill count); review study diary; assess adverse events; review inclusion/exclusion criteria; dispense study drug and diary

#### Study Visit 4 & 5 (6 and 9 months ± 15 days following initiation of intervention, respectively)

Review medical history, medications, and laboratory test results; symptom assessment; ECOG performance status; blood draw; MRI or CT for HCC surveillance; collect study drug and diary; assess compliance (pill count); review study diary; assess adverse events; review inclusion/exclusion criteria; interviewer-administered questionnaire (Visits 4 and 6 only); dispense study drug and diary

Review medical history, medications, and laboratory test results; symptom assessment; ECOG performance status; blood draw; MRI or CT for HCC surveillance; MRE with fat fraction or FibroScan for liver stiffness testing collect study drug and diary; assess compliance (pill count); interviewer-administered questionnaire; assess adverse events; review study diary

#### Endpoints - Evaluate the effect of pravastatin versus placebo after 12 months of treatment on:

- 1) Time to recurrence
- 2) Recurrence-free survival
- 3) Overall survival

- 4) Waitlist drop-off
  5) Change in liver stiffness
  6) Change in liver fat fraction
  7) Change in serum biomarkers of monocyte/macrophage and stellate cell activation
  8) Levels of liver tissue markers related to HCC

\*Blue box = standard of care clinical visit

## STUDY SUMMARY

Title	Pravastatin Intervention to Delay Hepatocellular Carcinoma Recurrence
Protocol Number	IIT2017-[name]-StatLv
Phase	Phase II
Methodology	Randomized, double-blinded, placebo-controlled, Phase II trial of statin to increase time to recurrence in patients with liver cirrhosis and initial hepatocellular carcinoma
Study Duration	5 years
Study Center(s)	Cedars-Sinai Medical Center (CSMC), Ronald Reagan UCLA Medical Center (UCLA), Northwestern Memorial Hospital (NWU), UCSF Medical Center (UCSF), Emory University Woodruff Health Sciences Center (EU)
	Primary Objective: To evaluate the effect of a pravastatin intervention versus placebo on the change in time to recurrence (TTR) from baseline to 12 months following treatment initiation.
Objectives	
 
Secondary Objective: To evaluate the effect of a pravastatin intervention versus placebo at 12 months from baseline on:
 
1) Recurrence-free survival
 
2) Overall survival
 
3) Waitlist drop-off
 
4) Change in liver stiffness
 
5) Change in liver fat fraction
 
6) Change in serum biomarkers of monocyte/macrophage and stellate cell activation
 
7) Levels of liver tissue markers related to HCC
 

Number of Subjects	130
Diagnosis and Main Inclusion Criteria	Patients with a confirmed diagnosis of liver cirrhosis (Child-Pugh A or B); current Model for End-Stage Liver Disease (MELD) < 30; Minimum 18 years of age; HCCs must fall within the Milan Criteria or OPTN tumor downstaging criteria; receipt of LRT with verification of adequate response; and patients whose lab results meet the inclusion criteria after the Screening visit blood tests.
Study Product(s), Dose, Route, Regimen	Pravastatin 40 mg and placebo identical in color, consistency, and appearance to pravastatin; oral administration daily (N=65 in each group)
Duration of administration	12 months
Statistical Methodology	Statistical analyses for the primary objective will be conducted on participants who complete the 12 month MRI or CT and blood specimen collection. The distribution of the clinical and demographical covariates, including but not limited to; age, race, smoking status, BMI, and comorbid conditions, will be summarized and compared between the intervention and control groups to assess the adequacy of the randomization. Chance differences between groups will be adjusted for using multiple regression modeling.

## 1.0 BACKGROUND AND RATIONALE

## 1.1 Study Disease

Hepatocellular carcinoma (HCC) is a highly lethal cancer with rising incidence and mortality rates. Approximately 33,000 HCC diagnoses were expected in 2016, and the incidence is increasing among the most rapidly of any cancer, with an age-adjusted annual increase of 3.7% and 2.9% in men and women, respectively (1). HCC burden depends heavily on age and ethnicity. Older Hispanic men have the highest HCC incidence rate of any major demographic group, and HCC risk overall is nearly 3 times higher in Hispanics compared to non-Hispanic whites (2). Tragically, HCC has a dismal 5-year survival rate of 18%, second in lethality only to pancreatic cancer (1). Thus, in-line with the incidence trends, HCC mortality is also increasing at the most rapid pace of any cancer and is highest in older Hispanic men (1, 3). Targeted studies of HCC in populations consisting of a high proportion of Hispanics are needed to identify strategies to curtail the rising HCC burden.

Between 70-90% of HCCs develop in people with liver cirrhosis, and cirrhosis is considered a pre-cancer lesion (4, 5). For a person with cirrhosis, the 5-year risk of developing HCC varies according to several influential characteristics including race/ethnicity, liver disease etiology, and severity of complications, with a cumulative HCC risk as high as 30% among patients with advanced cirrhosis (6-9). Hispanics have a more rapid progression from cirrhosis to HCC compared to other major racial/ethnic groups (10). Liver transplantation is the only curative option for cirrhosis and can prevent the development of HCC if patients can be transplanted in time. Over the last decade, there has been a growing crisis of insufficient donor livers for transplantation due to the convergence of increasing need, decreasing donation, and increasing discard of sub-optimal livers, leading to a near doubling of the median transplant wait time (11). Long wait times increase the chance for HCC development. Although patients who develop HCC are given priority on the waitlist and thus "advantaged" in the current system for liver allocation, between 10-15% of patients with cirrhosis who develop an HCC prior to receiving a transplant have a fatal recurrence of their cancer post-transplant (12).

The rising HCC burden has been attributed to the changing etiological landscape for HCC primarily brought on by the rising obesity pandemic. Obesity and diabetes are currently the leading risk factors for HCC, followed by alcohol abuse and hepatitis C virus (HCV) (13). Obesity (body mass index (BMI)  $\geq$  30) affects 34.9% of all adults and 42.5% of Hispanic adults; an overall increase of 2.8% from a decade ago (14). Nonalcoholic steatohepatitis (NASH), the hepatic manifestation of obesity and diabetes, is twice as common in Hispanics compared to non-Hispanic whites (15). NASH has more than doubled in incidence over the last decade, and it is projected that 25 million Americans will develop NASH by 2025, with 20% progressing to cirrhosis and/or HCC and may require liver transplantation (16-20). In summary, there is a rising problem of HCC which poses a substantial public health problem.

## 1.2 Study Agent

[figure not shown]

Figure 1. Molecular structure of pravastatin

Pravastatin (see Figure 1) is a lipid-lowering agent pravastatin is a derivative of ML236B (compactin), which was identified in a fungus called Penicillium citrinum in the 1970s. It is an inhibitor of 3-hydroxy-3-methylglutaryl-coenzyme A (HMG-CoA) reductase. This enzyme catalyzes the conversion of HMG-CoA to mevalonate, an early and rate-limiting step in the biosynthesis of cholesterol. The empirical formula of pravastatin is C23H36O7 and its molecular weight is 424.534 g/mol. Pravastatin sodium tablets, USP are available for oral administration as 10 mg, 20 mg, 40 mg, and 80 mg tablets. Inactive ingredients include: croscarmellose sodium. lactose

monohydrate, magnesium oxide, magnesium stearate, microcrystalline cellulose and povidone. The 10 mg tablet also contains ferric oxide red, the

20 mg and 80 mg tablets also contain ferric oxide yellow, and the 40 mg tablet also contains D & C yellow No. 10 aluminum lake & FD & C blue No. I aluminum lake.

Pravastatin a commonly prescribed HMG-CoA reductase inhibitor, which has a widely accepted tolerability profile with few serious side effects (21-23). Potential, but uncommon side effects include muscle, liver, and kidney problems. Elevated levels of creatine kinase and rhabdomyolysis occur in <1% of consumers, and myalgia, or muscle ache or weakness, can occur in approximately 5% of consumers (21-23). Historically, there has been reluctance to prescribe statins to patients with preexisting liver disease due to concerns regarding additional liver injury and diabetes (24). However, in recent years, the benefits of statin use have proven to substantially outweigh the minimal potential for adverse events in patients with liver disease: statins delay liver disease progression, improve survival, reverse non-alcoholic steatohepatitis, and ameliorate metabolic syndrome (25-28).

Despite the overall excellent hepatic safety profile of statins, underlying liver disease is a labeldefined contraindication. The hepatic safety of high dose pravastatin among 326 hyperlipidemic adults with well-compensated chronic liver disease was evaluated using a randomized, doubleblind, placebo-controlled, trial (29). Patients were randomized to daily pravastatin (80 mg) or placebo for 36 weeks. The primary safety endpoint was doubling of baseline alanine aminotransferase (ALT) values during 36 weeks of therapy. Overall, 8% of patients in the pravastatin group and 13% of patients in the placebo group experienced doubling of baseline ALT values during 36 weeks of therapy (P>0.05). These results have lessened the concern over an increased potential for statin-induced hepatotoxicity in patients with chronic liver disease. Furthermore, recommendations from National Lipid Association Statin Safety Task Force state that chronic disease and compensated cirrhosis are not contraindications for statin therapy (30).

Also, throughout the protocol, where we mention evaluation of medical contraindications to pravastatin we have included a clause "with the exception of active liver disease".

Lastly, with regards to liver function monitoring, we will test liver function 30 days after the initiation of therapy, then again after 60 days, and then once every 3-months for the duration of the trial. Based on data from the RCT in patients with compensated cirrhosis who were on high-dose pravastatin for 36 weeks, the frequency of our monitoring is adequate (29). Therapy will be stopped in any patient whose AST or ALT exceeds 5 times the institutional upper limit of normal (ULN).

Pravastatin is prescribed for primary and secondary prevention of cardiovascular disease and thus is indicated for long-term use. We will administer pravastatin 40 mg daily for 12 months in this trial.

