#### 3.1.1 Non-laboratory Measurements

**Imaging review.** Review of medical record by research coordinator to identify imaging required for eligibility purposes (see section 4.1.3 and 4.1.4) or all imaging studies conducted since eligibility or since the last study visit. Images will be sent to MedQIA (see 3.1.3) for central imaging review.

**Medical history.** Detailed medical history, including past medical/surgical interventions, disease history, and relevant laboratory results, obtained via patient interview and/or review of medical records by a study physician or research coordinator.

**Concomitant medications review.** Review of all current concomitant medications, including start and stop dates, dose, frequency, route, and indication (if available/applicable), obtained via review of the medical record or by patient self-report by a study physician or research coordinator.

**Medication compliance review.** Participants will be asked if they missed any doses of the study medication, and the dates of all missed doses will be recorded.

**Physical assessment**. Physician-directed physical assessment. Each assessment will include an interval symptom history; ECOG performance status assessment; vital signs, including blood pressure, heart rate, respiratory rate, and temperature; weight; and assessment of liver disease sequelae (varices, ascites and encephalopathy).

**Health assessment.** RN-directed assessment, consisting of ECOG performance status assessment and vital signs (including blood pressure, heart rate, temperature; and weight)

**Baseline symptom assessment.** Assessment of symptoms presenting prior to start of study intervention (Study Visit 1), obtained via review of the medical record or by patient self-report, by a study physician or research coordinator. NCI Common Terminology Criteria for Adverse Events version 5.0 (CTCAE v5.0) term, start and stop dates, grade, and treatment will be recorded on the Baseline Symptom Log. Grade should be determined by a study physician. Symptom assessment includes:

- Upper respiratory infection
- Headache
- Abdominal pain
- Constipation
- Nausea
- Vomiting
- Mild muscle aches
- Any other symptoms

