#### 6.2.2 Study Visit 1- Baseline Testing and Initiation of the Intervention

Study Visit 1 (Baseline measurements) will occur 0-30 days after the Screening Visit. The following procedures will be performed during this visit:

- Medical history
- Concomitant medication review
- Health assessment
- Clinical blood specimen
  - Blood chemistry
    - o Lipid
    - HbA1C
  - CPK
  - Research blood specimen
- Liver stiffness
- Liver fat fraction
- Baseline risk factor questionnaire

- Baseline symptom assessment
- Study agent
  - Dispense the study agent (one bottle of 120 capsules) and review instructions for how to take it
  - Dispense and review the study diary

## 6.2.3 Study Visit 2

Study Visit 2 will occur 1 month (± 15 days) after initiation of the Intervention. The following procedures will be performed during this visit:

- Symptom/adverse events assessment
- Medical history
- Concomitant medications review
- Health assessment
- Clinical blood specimen
  - Blood chemistry
  - o Lipid
- Imaging review
- Study agent
  - Collect study agent and diary
  - Assess compliance (pill count)
  - Review study diary
  - Dispense study agent (same bottle that was brought to the visit/collected for pill count)

## 6.2.4 Study Visit 3

Study Visit 3 will occur 3 months ( $\pm$  15 days) after initiation of the intervention (study drug initiation).

The following procedures will be performed during this visit:

- Symptom/adverse events assessment
- Medical history
- Concomitant medications review
- Health assessment
- Imaging review
- Study agent
  - Collect study agent and diary
  - Assess compliance (pill count)
  - Review study diary
  - o Dispense study agent (one new bottle of 120 capsules) and diary

## 6.2.5 Study Visit 4

Study Visit 4 will occur 6 months ( $\pm$  15 days) after initiation of the Intervention (study drug initiation). The following procedures will be performed during this visit:

- Symptom/adverse events assessment
- Medical history
- Concomitant medications review
- Physical assessment
- Clinical blood specimen
  - Blood chemistry
  - o Hba1c
  - $\circ$  AFP
- Research blood specimen
- Follow-up risk factor questionnaire

- Imaging review
- Study agent
  - Collect study agent and diary
  - Assess compliance (pill count)
  - Review study diary
  - Dispense study agent (one bottle of 120 capsules) and diary

## 6.2.6 Study Visit 5

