Study Visit 5 will occur 9 months ( $\pm$  15 days) after initiation of the intervention (study drug initiation). The following procedures will be performed during this visit:

- Symptom/adverse events assessment
- Medical history
- Concomitant medications review
- Health assessment
- Imaging review
- Study Agent
  - Collect study agent and diary
  - Assess compliance (pill count)
  - Review study diary
  - o Dispense study agent (one new bottle of 120 capsules) and diary

## 6.2.7 Study Visit 6

Study Visit 6 will occur 12 months ( $\pm$  15 days) after initiation of the intervention (study drug initiation). The following procedures will be performed during this visit:

- Symptom/adverse events assessment
- Medical history
- Concomitant medication review
- Physical assessment
- Clinical blood specimen
  - Blood Chemistry
    - o Lipid
    - o Hba1c
    - o PT/INR
    - o AFP
- Research blood specimen
- Imaging review
- Liver stiffness
- Liver fat fraction
- Follow-up risk factor questionnaire
- Study agent
  - Collect study agent and diary
  - Assess compliance (pill count)
  - Review study diary

**6.2.8** Unscheduled Visit (Transplant Specimen Collection). For all patients who enter the trial and receive a liver transplant before the end of this study, we will obtain specimens at the time of transplantation. The research blood specimen will be collected prior to transplant (while the patient is being prepped for surgery).

- Research blood specimen
- Transplant tissue specimen

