## 6.3 Follow-up telephone contact

Clinical research staff will make follow-up telephone calls to study participants on days 30  $\pm$  7, 60  $\pm$  7, and 90  $\pm$  7 after completion of Study Visit 6 (or earlier if study agent discontinued prior to completion) to assess symptoms and adverse events.

		Month 0	Month 1	Month 3	Month 6	Month 9	Month 12	30, 60, 90 days	Unscheduled Liver
Study Activity/Measurement	Screen 1	Study Visit 1	Study Visit 2	Study Visit 3	Study Visit 4	Study Visit 5	Study Visit 6	Follow-up Calls ^	Liver Transplant %
Review subject eligibility criteria	Х								
Obtain informed consent and HIPPA authorization	Х								
Pregnancy test	Х								
Imaging review	Х		Х	Х	Х	Х	Х		
Registration/randomization	Х								
Medical history		Х	Х	Х	Х	Х	Х		
Concomitant medication review		X	Х	Х	Х	Х	Х		
Physical assessment	Х				Х		Х		
Health assessment		Х	Х	Х		Х			
Baseline symptom assessment		Х							
Blood chemistry	Х	Х	Х		Х		Х		
Prothrombin time	Х						Х		
Creatine kinase		Х							
Hemoglobin A1c (glycated hemoglobin)		Х			Х		Х		
Lipid panel		Х	Х				Х		
Serum AFP test	Х				Х		Х		
Liver stiffness		Х					Х		
Liver fat fraction		Х					Х		
Research blood specimen		Х			Х		Х		Х
Baseline risk factor questionnaire		X							
Follow-up risk factor questionnaire					Х		Х		
Dispense study drug and diary with instructions		Х	Х	Х	Х	Х			
Symptom/adverse event assessment			Х	Х	Х	Х	Х	Х	
Collection and review agent and diary, assess medication compliance			Х	Х	Х	Х	Х		
Telephone contact #	Х			Once a	a Month			Х	Х
Transplant tissue specimen									Х

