## 6.5 Clinical Laboratory Minimum Test Requirements

Blood Chemistry	Lipid Panel	Other Blood Tests
Alanine aminotransferase	Total cholesterol	Hemoglobin A1C (HbA1C)
(ALT (SGPT))	High density lipoprotein (HDL)	Creatine phosphokinase
Aspartate aminotransferase	cholesterol	(CPK)
(AST (SGOT))	Low density lipoprotein (LDL)	Prothrombin Time (PT/INR)
Alkaline phosphatase (ALP)	cholesterol	Alpha-fetoprotein (AFP)
Bilirubin, total	Triglycerides	
Creatinine		
Glucose		
Sodium		

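### Section 1.2 commits to roughly quarterly liver tests, but the visit lists and Schedule of Events omit blood chemistry at months 3 and 9

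*Combined protocol and SAP*

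**What the plan says.** Section 1.2 (Study Agent) gives the liver-test plan: "we will test liver function 30 days after the initiation of therapy, then again after 60 days, and then once every 3-months", continuing for the length of the trial. It cites the earlier 36-week randomised trial of high-dose pravastatin in chronic liver disease and concludes that "the frequency of our monitoring is adequate". It also stops therapy in any patient whose AST or ALT goes above 5 times the institutional ULN.

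The study schema lists for Visit 3: "Review medical history, medications, and laboratory test results; symptom assessment; ECOG performance status; blood draw; MRI or CT for HCC surveillance". It uses the same items for Visits 4 and 5.

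Section 6.5 places "Alanine aminotransferase" and AST in the blood chemistry panel. In 6.2.3 to 6.2.7 that panel is listed at Visits 2, 4 and 6. The entries that begin "Study Visit 3 will occur 3 months" (6.2.4) and "Study Visit 5 will occur 9 months" (6.2.6) list no clinical blood specimen. In the Schedule of Events the row "Blood chemistry" is marked at screening and months 0, 1, 6 and 12, and is blank at months 3 and 9.

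Section 5.4 requires permanent discontinuation for ALT or AST above 5 times ULN only when the rise is judged at least possibly related to the study agent. Its temporary hold for events of grade 3 or higher carries the same condition.

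**The concern.** Section 1.2 acknowledges that liver disease is a labelled contraindication to pravastatin, and the monitoring plan is part of its case for treating these patients anyway. The adequacy statement is attached to the frequency given there. Coordinators, however, work from the visit lists and the schedule table, and a site that follows those will not produce the tests 1.2 describes. Whether an ALT or AST value exists around months 3 and 9, so that the 5 times ULN rule can be applied, then depends on laboratory work done for other reasons.

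The two statements of the stopping rule also need harmonising. A site reading only 5.4 has no instruction to stop for a rise judged unrelated. Sections 6.6 and 6.7 allow a stop in that case but do not require one.

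**Working it through.** No sample-size or power figure is involved. The check compares the sections and counts tests.

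**1. What 1.2 implies.** The first test is at day 30. Sixty days after that is 30 + 60 = day 90, or about month 3. Testing every 3 months from there gives months 6, 9 and 12. The result is months 1, 3, 6, 9 and 12: 5 tests, on the dates of Visits 2 to 6. Gaps from baseline are 1, 2, 3, 3 and 3 months.

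If 60 days is counted from initiation instead, the tests fall at days 30, 60, 150, 240 and 330 (5 tests). If day 60 is added to the quarterly visits, they fall at months 1, 2, 3, 6, 9 and 12 (6 tests). Neither of these matches the visit calendar. The only contact near day 60 is the monthly telephone call in 6.2.1, which includes no laboratory test.

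**2. What the visit lists and schedule give.** Months 1, 6 and 12: 3 tests. Gaps from baseline are 1, 5 and 6 months. With windows of 15 days either side, the last gap can reach 6 months plus 30 days, about 7 months.

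**3. The difference.** 5 − 3 = 2 tests, at months 3 and 9. The month-12 test coincides with the end of dosing and can hardly trigger a stop. The tests that can act on treatment are therefore 2 (months 1 and 6) against 4 (months 1, 3, 6 and 9).

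**4. Treatment time more than 3 months after the last listed test, if the visit lists govern.** (5 − 3) + (6 − 3) = 5 of 12 months, 42%. If 1.2 governs, or the schema draws are chemistry, it is 0 of 12. The documents leave the present position somewhere in that range.

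**5. What the schema draw is likely to be.** The schedule places research blood at months 0, 6 and 12 and at transplant, so a draw at month 3 or 9 is not the research specimen. At Visit 2 the schema uses the same words, and 6.2.3 there specifies chemistry and lipids. The likely meaning is clinical blood at Visits 3 and 5 that was left out of the lists and table. This is an inference, because the schema names no panel.

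**6. The two stopping statements side by side.** For a related rise above 5 times ULN, 1.2 says stop and 5.4 says discontinue permanently. For an unrelated rise, 1.2 says stop, and 5.4 neither requires nor forbids it. A site can comply with both by stopping for every rise and making the stop permanent for related ones.

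**The case against.** The strongest reply is that the requirement already exists. Section 1.2 is protocol text, 10.6.1 requires conduct exactly as the approved protocol describes, and the schema supports quarterly blood. This stands in part. It would be wrong to infer that the protocol contains no requirement for tests at months 3 and 9. The documents conflict, and no rule says which section prevails. That is a reason to correct the lists and table, since they are what sites execute.

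A second reply is that chart results will fill the gap. Visits 3 and 5 include a medical history, which covers "disease history, and relevant laboratory results, obtained via patient interview and/or review of medical records by a study physician or research coordinator", and 4.5 says study visits will be coordinated with usual-care tests where practical. This also stands in part: existing results will be seen, but the visit lists do not make one exist. Section 4.4 admits patients who are inactive on the waitlist or ineligible for transplant, so uniform usual-care testing cannot be assumed. The documents do not say how often results would be available.

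Third, an abnormal laboratory finding counts as an adverse event (7.3.1), and adverse events are followed whatever their attribution (7.2). That covers a rise once it has been seen; it does not schedule a test.

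A reader might infer that patients go unmonitored for 5 or 6 months, or that the sparser schedule is unsafe. The documents support neither. The 42% measures distance from a listed test. Section 7.1 recommends testing before treatment and then as clinically indicated, and even the sparser schedule, with screening and baseline tests, exceeds that. A reader might also take the stopping rules in 1.2 and 5.4 to be incompatible; as the working shows, they can be followed together.

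**Conclusion.** The conflict is real and should be fixed. Section 1.2 and the schema point to liver tests at months 1, 3, 6, 9 and 12. The visit lists and Schedule of Events carry only months 1, 6 and 12, so a site following them delivers 3 of 5 on-treatment tests, with a longest nominal gap of 6 months instead of 3.

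The count of 5 rests on reading the 60 days as running from the first test. The other readings give 5 or 6 tests, and the lists fall short of those as well. The 5-of-12-months figure holds only if the lists govern. The finding concerns consistency of safety monitoring; it is not evidence of harm, and the analysis is untouched. The stopping-rule difference is a secondary matter of harmonisation.

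**What to change.** 1. Add a clinical blood specimen with blood chemistry to Visits 3 and 5 (6.2.4 and 6.2.6), and mark months 3 and 9 in the schedule row. Accept chart results from the past 30 days, as 3.1.2 already does. In 1.2, replace the 60-day phrase with month 3.

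2. If the sparser schedule is what the sponsor wants, change 1.2 to months 1, 6 and 12, and remove or re-justify the adequacy sentence.

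3. In 5.4, add a hold for any AST or ALT above 5 times ULN regardless of attribution, and keep permanent discontinuation for related rises. Do not narrow 1.2 to related rises by default, since that would remove the more protective stop.

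**Cost.** A protocol amendment. Item 1 adds at most 2 × 130 = 260 chemistry panels, some extra blood draws and no new visits. The share of patients with a chart result within 30 days is not given; assuming 0%, 50% or 100%, the number is 260, 130 or 0. Item 2 is text only. Item 3 may add some dose interruptions; the documents do not allow an estimate of how many.
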